## **RESEARCH QUESTIONS**

- 1) Is it possible to adapt Learning Together for primary schools?
- 2) Is progression to a phase III RCT justified in terms of pre-specified criteria?
- 3) Are outcome and covariate measures well completed and reliable?
- 4) Which methods to survey teachers are most feasible?
- 5) With what rates are schools recruited and retained?
- 6) What do qualitative data suggest about how context influences implementation and about refinements to the theory of change?
- 7) Are any potential harms suggested and how might these be mitigated?
- 8) What is treatment as usual in control schools and is there any evidence of contamination between arms?
- 9) Are methods for economic evaluation feasible?

## **PUBLIC AND POLICY INVOLVEMENT AND ENGAGEMENT**

PPIE is central to the project. The PPIE lead for the project will be [name] who is an ex-teacher and mother of two school children. She previously worked as lead facilitator on Learning Together and is now freelance. She has experience facilitating workshops and coaching with children and teachers as well as community volunteering. We wanted to list [name] as a co-investigator but the online system did not enable this.

PPIE conducted so far with senior leaders and teachers from five primary schools in south-east England indicates that: bullying and poor mental wellbeing are highly prevalent and worse post-pandemic; schools lack scalable, effective bullying prevention interventions; schools would struggle to implement curriculum-based interventions because of lack of timetable space; interest in restorative practice is high; some schools are already conducting restorative practice but without training or support materials so fidelity to restorative practice best practice is likely to be poor; schools need training and guidance materials to deliver restorative practice properly; and schools are enthusiastic about using action groups, student involvement and data on student needs to inform action.

Phase 1 will involve PPIE-based adaptation involving two schools, plus a group of children recruited from other primary schools and a group of parents to provide broader views. The approach to PPIE in phase 1 is described in detail in the relevant section below. One teacher not working at a school involved in the pilot RCT will be invited to sit on the study steering committee. Phase 1 will also involve us consulting with the above teachers and students to inform how we conduct student surveys, which we anticipate will be via paper questionnaires with fieldworkers reading out questions and response options.

In phase 2, we will consult twice with a group of policy stakeholders about our emerging findings and methods. We include letters of support from organisations indicating that they are already willing to participate in these groups. One meeting in the middle of the project will review emergent finding from the process evaluation and critically appraise drafts of the follow-up questionnaires. The meeting near the end will focus on interpretation and dissemination of our results, and the value of proceeding to a phase III RCT of the intervention.

## **RESEARCH PLAN/METHODS**

## **Project objectives and timetable**

1. To undertake PPIE with various stakeholders, evidence review and a survey of schools in south-east England to inform adaptation of Learning Together for primary schools (Dec 2023-Sep 2024).
2. To recruit six schools for the pilot RCT, conduct baseline student and teacher surveys, and randomise schools (May-July 2024).
3. To implement the intervention to all students in the four intervention schools (Sep 2024-Jul 2025).
4. To conduct process evaluation (Sep 2024-Jul 2025).
5. To conduct follow-up student and teacher surveys (repeat cross-sectional design) 12 months post-baseline (May-July 2025).
6. To analyse data (Aug-Sep 2025).
7. To disseminate findings and assess progression to phase III RCT (from Oct 2025).

Timing of the pilot trial allows a start-up phase between allocation and delivery so schools can organise staffing and activities, as suggested by previous trials.

### **Phase 1: Adaptation**

Adaptation of the Learning Together intervention for primary schools will occur from December 2023 to September 2024. This will be underpinned by PPIE with various stakeholders, a review of systematic reviews of whole-school and restorative practice interventions in primary schools and an online survey of schools in SE England.

Phase 1 will involve PPIE-based adaptation involving staff and students from 2 primary schools. These schools will have high free school meal entitlement (indicating high need) and good/outstanding Ofsted ratings (indicating high capacity to collaborate). Adaptation will involve 3 sessions at each school reviewing existing Learning Together materials (December 2023) and successive drafts of adapted materials (March and April 2024). Each session will involve a workshop with 10 year-5/6 students (diverse by gender, ethnicity and school engagement) and a workshop with 5 staff (diverse by role/seniority). Adaptation will also involve: two meetings with another group of 10 children recruited from other primary schools; and one meeting with a group of parents. Children will be recruited in pairs from 5 different schools. One teacher not working at a school involved in the pilot RCT will be invited to sit on the study steering committee. Phase 1 will also involve us consulting with the above teachers and students to inform how we conduct teacher and student surveys.

The review of systematic reviews will address the following questions: (1) are there additional intervention components (including social and emotional skills curricula) that are elements of effective primary school bullying prevention interventions, which are consistent with the theory of change for the Learning Together Primary Schools intervention and which could be feasibly and usefully incorporated into the intervention?; (2) are there factors influencing the feasibility, acceptability, reach or effectiveness of primary school bullying prevention interventions that should be considered in adapting Learning Together for primary schools; (3) are there feasible, acceptable and reliable methods of surveying primary school teachers and students reported in evaluations of primary school bullying prevention interventions that could usefully inform the choice of methods for the pilot trial?; (4) do evaluations of primary school bullying prevention interventions use parental opt-out or opt-in consent?; and (5) do evaluations of primary school bullying prevention interventions suggest any amendments to the proposed methods for the pilot RCT?

The online survey of primary schools in SE England will address the following questions: (1) are the intervention components and methods we propose to include in Learning Together

Primary schools feasible and acceptable to implement in English primary schools?; (2) do English primary schools already deliver any of these components and if so with what training, facilitation or other support?; (3) do English primary schools deliver social and emotional skills curricula and, if so, which ones, comprising how many lessons and targeting which students?; (4) how much would English primary schools be prepared to pay for an effective bullying prevention intervention?; (5) are the evaluation methods proposed for the pilot RCT feasible and acceptable to conduct; and (6) would schools potentially be interested in participating in a pilot or phase III trial of this intervention?

The study will then progress to phase 2 dependant on the following criteria being met: (to be judged by the study steering committee): (1) have feasible and acceptable methods for surveying students and teachers in the pilot RCT been identified?; (2) has a decision been made as to whether parental opt-in or opt-out consent is appropriate for the pilot RCT?; (3) have fidelity and acceptability metrics been developed which will inform the evaluation methods and progression criteria for the pilot RCT?; (4) have all other evaluation methods for the pilot RCT been finalised?; (5) has a decision been made as to whether or not the intervention to be piloted should include a social and emotional skills curriculum?; (6) has the intervention to be piloted been adapted for primary schools?; (7) have all intervention materials and processes been elaborated?; (8) have PPIE members been recruited to sit on the study steering committee for the pilot RCT?; and (9) have all of the above questions been appropriately informed by the evidence review, schools survey and PPIE?

## **Phase 2: External pilot cluster RCT**

### ***Design overview***

The external pilot cluster RCT will occur in six primary schools (four intervention, two control). Recruitment, baseline surveys of students and teachers, and randomisation will occur in April-July 2024. Schools will be randomly allocated 2:1 to intervention/control (1:1 in phase III RCT) stratified by free school meals (plus Ofsted rating in phase III RCT) in June/July 2024. A 2:1 allocation will allow us to pilot randomisation while ensuring diversity across four schools for intervention piloting. The intervention will be implemented in the four intervention schools from September 2024 to July 2025. The pilot RCT will include an integral process evaluation and economic evaluation feasibility study (figure 2) occurring during this time. Follow-up surveys will occur in June/July 2025. The primary outcome for the pilot RCT will be assessing criteria for progression to a phase III RCT. Primary and secondary outcome measures for a phase III RCT will be assessed for completion and reliability but effects on these outcomes will not be assessed. These outcomes are described in detail below but consist of twin primary outcome measures assessing student-reported bullying victimisation and perpetration in the past two months, plus secondary outcomes consisting of: adult-reported social and emotional problems; student-reported cyber-bullying victimisation; student-reported wellbeing at school; routine data on student attendance/attainment; teacher-reported student behaviour; teacher-reported self-efficacy; and teacher-reported burnout.

Any future phase III RCT would involve a repeat cross-sectional RCT design drawing on data from students in years 3-6 (age 7-11) at baseline and follow-up. This design is chosen rather than a longitudinal cohort-based RCT for three reasons. First, the design allows for 36-month follow-up (which is the time period over which impacts are likely to be generated according to the trial of Learning Together) without the need to track older students into secondary school (which would result in significant attrition). Second, literature suggests that, in school cluster RCTs with significant in/out migration, the baseline cohort will not remain representative and this is a greater issue in primary than secondary schools. Third, statistically this design offers comparable power in analysis of binary outcomes. A final decision on phase III design will be made in light of the pilot.

### **Settings/context**

Learning Together Primary Schools is intended to be deliverable in all English primary schools (including faith schools, free schools, academies and private schools) excluding pupil referral units, schools for those with special educational needs and disabilities, and schools with 'inadequate' Ofsted inspections (which previous studies indicate lack the capacity to deliver until they gain an improved inspection report). We will recruit primary schools in south-east England which include years 3-6. This geographical spread is appropriate for the pilot RCT to reduce travel time and costs. Schools will vary by free school meals (measure of poverty), Ofsted rating (measure of school capacity) and school type so we can assess feasibility across factors likely to affect this. Any future phase III RCT would be national in scope and would also include a representative variety of school types.

### **Study population**

The study population is defined as students in years 3-6 (aged 7-11 years) as well as their teachers at baseline and follow-up during the trial. All student-reported measures are suitable for students in the age range being examined here (see outcome measures below). No students deemed competent to complete data collection will be excluded from research recruitment unless they do not assent to the research or parents withdraw them from the research. Those who have mild learning disabilities or limited English will be supported to complete the questionnaire by researchers.

### **Analytic sample and sample size**

The pilot focuses on feasibility and no power calculation is performed. Instead, the pilot RCT aims to include sufficient diversity of schools in terms of free school meals and Ofsted rating to allow piloting of the feasibility and acceptability of the intervention in a diverse range of contexts.

For the phase III RCT, to detect an effect of  $RR=0.8$  on bullying victimisation at 80% power and 5% significance will require 30 schools per arm assuming 160 students per school, drop-out of one school per arm, 25% bullying victimisation in control schools and an intra-cluster correlation coefficient (ICC) of 0.02 for victimisation. Our effect size is a relatively conservative one, slightly larger than that detected in the Learning Together trial but smaller than the effect sizes reported in recent systematic reviews of school-based bullying prevention on bullying perpetration ( $OR=1.31$ : 95% confidence interval (CI) 1.24, 1.38) and victimization ( $OR=1.24$ : 95% CI 1.19, 1.31) across school settings. Our estimated effect size is certainly of policy significance. The effect size takes into account recent evidence that bullying prevention is more effective when delivered to younger students, which is plausible given that early intervention in primary schools, as bullying behaviours manifest, would be expected to be more effective than prevention in secondary schools. Student numbers per school, prevalence and ICC are now informed by recent UK research and in line with broader estimates. Our pilot will provide a check on our assumptions about prevalence of the outcome and ICC while acknowledging small sample limitations. Our pilot will not assess preliminary intervention effects since it is not powered to do so.

### **Recruitment and randomisation**

We will recruit primary schools in south-east England inclusive of years 3-6. Schools will vary by free school meals (measure of poverty), Ofsted rating (measure of school capacity) and school type so we can assess feasibility across factors likely to affect this. As with our previous trials, schools will be recruited by a combination of emails and phone calls to schools, local authorities, school networks and academy chains. Response rates will be recorded, as will any stated reasons for non-participation.

As explained above, after baselines, schools will be randomly allocated 2:1 to intervention/control (1:1 in phase III RCT) by LSHTM clinical trials unit (CTU), stratified by free school meals (plus Ofsted rating in phase III RCT). A 2:1 allocation in the pilot RCT

will enable us to pilot randomisation while ensuring sufficient diversity of schools in the intervention arm for intervention piloting. Piloting randomisation is necessary given the paucity of UK RCTs of primary school bullying prevention. Schools will be given unique study numbers to preserve allocation concealment within the CTU. The CTU will inform the fieldwork team of allocations who will then inform schools. Informed by the Positive Choices and 'If I Were Jack' RCTs, we will incentivise recruitment and retention by offering a £500 payment to all schools with an additional £1,000 for those allocated to the intervention group, reflecting the greater research load on such schools. Previous studies suggest that payment is now absolutely essential for maintaining school participation in research particularly in the current context of current stretched school budgets and institution strain. Each school will be allocated a named research liaison contact to facilitate retention.

### ***Intervention and comparator***

The **Learning Together Primary Schools** intervention is described below using the TIDieR framework and in figure 1.

***Theory of change:*** Learning Together is a whole-school restorative practice intervention the theory of change of which is informed by the theory of human functioning and school organisation. Restorative practice aims to prevent/resolve face-to-face and online conflicts between students or conflicts between staff and students to prevent further harms and improve student/student and student/staff relationships. Learning Together aims to reduce bullying and social and emotional problems via two mechanisms: a) using restorative practice to improve relationships and prevent/de-escalate conflict; and b) using an action group to involve students in school decisions and build school belonging. Existing studies suggest mechanism a) will be key in schools with lower capacity while b) will be key in schools with higher capacity.

***Materials:*** Schools will receive an anonymised report on overall student needs (drawing on baseline survey), an intervention manual and a workbook to help teachers run restorative practice sessions. In the previous RCT, the curriculum was poorly implemented and did not contribute to effectiveness. Initial PPIE to inform this proposal suggests that primary schools already deliver classroom social and emotional learning. Not including this component would also enable the study to better establish the specific effectiveness of restorative practice. However, including this component may increase the potential effectiveness of the overall intervention. Consultation will inform a final decision on whether the intervention in a phase III RCT should include a curriculum component in phase 1. If it is determined in the adaptation phase that the intervention should involve a curriculum, schools will be provided with lesson plans and slides.

***Training/facilitation:*** All school staff will receive a two-hour introductory training in restorative practice. Selected 4-5 staff per school will receive three-day in-depth training provided by L30 Relational Systems (training partner in previous Learning Together RCT). The Place2Be charity will facilitate action groups. If it is determined in the adaptation phase that the intervention should involve a curriculum, schools will be provided with additional training for this.

***Procedures, delivery & dose:*** All staff will undertake restorative practice in their tutor groups and classrooms to prevent conflict and respond to minor incidents coming to their attention. Selected staff will facilitate restorative practice conferences in response to more serious incidents which they identify. The action group will meet termly and: review needs data to decide local priorities; identify staff to be trained; revise rules/policies to support restorative practice; and plan communications to students/parents. The action group will include approx. six staff (diverse by seniority/role) and eight students from years 3-6 (also diverse by gender, ethnicity, school engagement). If it is determined in the adaptation phase that the intervention should involve a curriculum, schools will deliver this in lesson time.

Planned adaptations: Guided by the manual and needs data, schools will identify local priorities re. the forms of bullying to be addressed and the student groups most affected.

Cost: £1500 per school met from sources other than schools for the pilot.

The intervention described above complements existing activities.

The **comparator** will be treatment as usual with schools continuing with existing activities to prevent bullying and student social and emotional problems. Process evaluation will describe this. Initial PPIE suggests that some schools already use restorative practice but few use a whole-school approach or are guided by training/materials.

### **Outcome measures**

#### Pilot outcomes

For this pilot trial, the primary outcome is assessment of criteria for progression to phase III RCT according to the following criteria:

| Criterion number | Red/amber/green criteria  |  |  |
|------------------|---|--|--|
|                  | Red*   | Amber**   | Green***  |
| 1.               | Recruitment and randomisation do not occur within the allocated timescales  | Recruitment and randomisation occur within the allocated timescales  | Recruitment and randomisation occur within the allocated timescales  |
| 2.               | <4 schools are retained in study  | 4 schools are retained in study  | ≥5 schools are retained in study   |
| 3.               | Intervention is implemented with <70% fidelity in ≥2 schools retained in intervention arm                                       | Intervention is implemented with <70% fidelity in 1 school retained in the intervention arm  | Intervention is implemented with ≥70% fidelity in all schools retained in the intervention arm                                       |
| 4.               | Intervention is acceptable to <70% of teachers and students responding to the survey in ≥2 schools retained in intervention arm | Intervention is acceptable to <70% of teachers and/or students responding to the survey in 1 school retained in the intervention arm | Intervention is acceptable to ≥70% of teachers and students responding to the survey in all schools retained in the intervention arm |
| 5.               | Student response rates and completion of outcome measures are   | Student response rates and completion of outcome measures are  | Student response rates and completion of outcome measures are  |

|    | <80% in ≥3 schools retained in the study   | <80% in 1-2 schools retained in the study   | ≥80% in all schools retained in the study   |
|----|--|---|---|
| 6. | Staff response rates and completion of outcome measures are <70% in ≥3 schools retained in the study | Staff response rates and completion of outcome measures are <70% in 1-2 schools retained in the study | Staff response rates and completion of outcome measures are ≥70% in all schools retained in the study |
| 7. | There is evidence of substantial contamination between arms  | There is evidence of some contamination between arms  | There is no evidence of any contamination between arms  |

\* Any red criteria indicate that the study will not progress to a phase III trial.

\*\* Any amber criteria indicate that the study might be able to progress to a funding proposal for a phase III trial if mitigating factors are identified and implemented.

\*\*\* Indicating the study should be recommended to progress to a funding proposal for a phase III trial.

The precise metrics that will be used to assess implementation fidelity and acceptability will be defined in phase one when the intervention is finalised. These will be shared with the study steering committee and with NIHR for approval. The NIHR will make judgements about how the study has met the above criteria informed by assessments made by the study steering committee.

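### Progression criteria 3 and 4 count only retained intervention schools, so a non-delivering school can improve the grade by leaving; criterion 2 ignores arm

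*Protocol*

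**What the plan says.** The Protocol's Design overview randomises six schools, four to intervention and two to control. The Pilot outcomes section makes the assessment of seven progression criteria the primary outcome. Any red means no progression. Any amber means progression is possible if mitigation is found and put in place. Green means progression should be recommended.

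- **Criterion 2 (retention):** red if "<4 schools are retained in study", amber if "4 schools are retained in study", green if "≥5 schools are retained in study". No arm is named.
- **Criterion 3 (fidelity):** green if "Intervention is implemented with ≥70% fidelity in all schools retained in the intervention arm". Amber is one retained intervention school below 70%; red is two or more.
- **Criterion 4 (acceptability):** the same retained-school denominator in all three bands, restricted further to survey responders.
- **Criterion 7 (contamination):** green if "There is no evidence of any contamination between arms".

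Retention is not defined. The text below the table leaves the fidelity and acceptability metrics to phase 1 and the final judgement to NIHR, informed by the steering committee. Nothing in the Protocol says how a withdrawn school is scored on criteria 3 or 4, or requires any control school to remain.

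**The concern.** Fidelity and acceptability are there to show whether primary schools can and will deliver this intervention. A school that withdraws because it could not deliver, or did not want to, is the clearest evidence against that. Conditioning both criteria on retention removes that evidence, so the same delivery failure can earn a better colour when the school leaves than when it stays.

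Retention is the only criterion left to register the loss, and it tolerates one lost school at green and two at amber, whichever arm they come from. With only two controls, the whole comparison arm can go within the amber band. At stake is whether the decision to seek funding for a phase III trial rests on all the schools randomised to the intervention or only on those that stayed.

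**Working it through.** **Inputs.** Four intervention and two control schools (Design overview). Colour bands for criteria 2 and 3 (Pilot outcomes). The plan gives no figure of its own to reproduce here; this is a check of a decision rule.

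**Rule as written.** Let F be the number of intervention schools that cannot reach 70% fidelity, L the number of those that leave, and C the number of controls lost.

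- Schools retained = 6 − L − C. Criterion 2 is red below 4, amber at 4, green at 5 or 6.
- Retained schools below 70% = F − L. Criterion 3 is green at 0, amber at 1, red at 2 or more.
- Comparison: criterion 3 over all four randomised intervention schools, using F in place of F − L.

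All other criteria are taken as passed. Criterion 1 is read as green because its amber and green cells have the same wording.

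| F | L | C | Retained | Crit. 2 | Crit. 3 as written | Crit. 3, all four | Overall as written | Overall, all four |
|---|---|---|---|---|---|---|---|---|
| 1 | 0 | 0 | 6 | green | amber | amber | amber | amber |
| 1 | 1 | 0 | 5 | green | green | amber | **green** | **amber** |
| 1 | 1 | 1 | 4 | amber | green | amber | amber | amber |
| 2 | 0 | 0 | 6 | green | red | red | red | red |
| 2 | 1 | 0 | 5 | green | amber | red | **amber** | **red** |
| 2 | 2 | 0 | 4 | amber | green | red | **amber** | **red** |
| 2 | 2 | 1 | 3 | red | green | red | red | red |
| 3 | 3 | 0 | 3 | red | green | red | red | red |
| 0 | 0 | 2 | 4 | amber | green | green | amber | amber |

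Rows 1 and 2 describe the same failure: leaving turns amber into green. Rows 4 and 6 do the same for two schools: leaving turns red into amber. From three leavers on, criterion 2 is red in any case. Criterion 4 follows the same pattern, since a school that has left contributes no retained-school result.

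**Illustration of frequency.** The documents give no withdrawal rate, so p is an assumption: each intervention school independently fails and leaves with probability p, no failing school stays, both controls stay, and all else passes. Misgrading then occurs with exactly one or exactly two leavers:

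P = 4p(1 − p)³ + 6p²(1 − p)²

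- p = 0.05: 0.171 + 0.014 = 0.185 (about 19%)
- p = 0.10: 0.292 + 0.049 = 0.340 (34%)
- p = 0.25: 0.422 + 0.211 = 0.633 (63%)

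At p = 0.25, three or four leavers have probability 0.051; those pilots are correctly red through criterion 2.

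**Loss of controls.** The last row keeps all four intervention schools and no control. Criterion 2 is amber, as for any other loss of two schools. The section on the comparator and contamination relies on one senior-staff interview per control school plus the student and staff surveys. If those are missing at follow-up, criterion 7 could be read as green simply because nothing was observed.

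**The case against.** The best defence is that withdrawals are not hidden. Criterion 2 counts them, research question 5 asks for school retention rates, and the Data analysis section reports retention in a CONSORT diagram. Amber is not a pass, since mitigation is required. NIHR judges the criteria with steering committee input, and the Version control table records that the SSC and DMEC approved the traffic-light criteria. The metrics are still to be set in phase 1, and schools are paid to stay.

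Part of this stands. Committee discretion limits the harm, and this is a small feasibility pilot that tests no effects. But discretion and a flow diagram change no colour, and only the metrics are deferred: the school denominators are already written into the table.

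Several stronger readings are tempting, and the documents do not support them:

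- **That a departing school guarantees all green.** It only makes green possible; every other criterion must also pass. Because retention is undefined, a school that stops delivering but stays in data collection could still be counted and scored below 70%.
- **That every pilot with two or more leavers is misgraded.** With three or more, criterion 2 is already red. Two leavers plus one lost control is also red.
- **That criterion 7 turns green once both controls leave.** Control data gathered before withdrawal might be used, and no text says that an unassessable criterion counts as green.
- **That failing schools are the likeliest to leave.** The Protocol gives no figure for this, and the argument does not need it.

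**Conclusion.** The point holds as a defect of the written rule, at the level of should-fix. With one leaver and both controls kept, the overall grade can be green where counting all four randomised schools gives amber. With two leavers and both controls kept, it can be amber where counting all four gives red. With three or more leavers the overall grade is unaffected. These results follow from the table alone, provided that the leavers could not deliver, exit the study or arm completely, and the remaining schools pass everything else.

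The 19%, 34% and 63% figures are illustrations resting on assumed rates of 5%, 10% and 25%, independence between schools and no control losses. They are not estimates for this trial. Separately, loss of both controls is graded no worse than any other loss of two schools, and criterion 7 has no rule for missing control data.

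**What to change.** 1. **Criterion 3:** assess over all four randomised intervention schools. Count a school that withdraws as below 70%, unless records show that at least 70% of the components due by then were delivered and the documented reason is unrelated to the intervention. Report a school that leaves for unrelated reasons before any component is due as not assessable.
2. **Criterion 4:** count a withdrawn school as not acceptable when its documented reason relates to the intervention; otherwise report it as not assessable. Delivery records should not decide this criterion, because they measure fidelity.
3. **Retention:** define it, separating withdrawal from the intervention from withdrawal from data collection.
4. **Criterion 2:** report by arm, with a grade agreed with the SSC and DMEC that separates loss of both controls from other losses of two schools.
5. **Criterion 7:** grade as not assessable, not green, when no control-school data are available.

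The cost is a change of table wording with SSC and DMEC agreement, the route already used for version 1.3. The criteria become slightly stricter, and reasons for withdrawal must be documented. One withdrawal may register under criteria 2, 3 and 4, but the colours are not summed: any single red or amber sets the outcome, so this does not compound.
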